#### Analysis of Co-primary Efficacy Endpoints

The primary analysis of SRI-4 response at Week 52 among all subjects in the primary analysis cohort, and SRI-6 response at Week 52 among HDA subjects in the primary analysis cohort, will be an estimate of OR, together with associated two-sided 95% CI and p-value (testing null hypothesis  $H_0$ : OR = 1.0), comparing each M2951 dose group to placebo, based on a logistic model for the odds of a given SRI response in the appropriate population, with M2951 dose group or placebo group as a factor and adjustment for covariates based on randomization strata. The primary analysis of the co-primary efficacy endpoints will be based on the modified intent-to-treat (mITT) analysis set.

Descriptive statistics for SRI-4 response, and for SRI-6 response in the HDA subgroup, will be provided for each treatment group by time point.

#### Analysis of Key Secondary Endpoints

Time to first severe (BILAG A) flare during the Treatment Period in all subjects will be compared between M2951 and placebo via a stratified log rank test. The adjusted hazard ratio comparing M2951 to placebo will be estimated (together with 95% CI) via a Cox regression model, with treatment group as a factor, and controlling for covariates defining randomization strata. A subject who discontinues treatment or completes treatment without experiencing severe flare will have his/her time to flare censored at the last time point at which flare could be assessed.

Kaplan-Meier estimates of probability of surviving free of severe (BILAG A) flare as a function of time on treatment will be provided for each treatment group.

The analysis of SRI-4 response at Week 52 among serologically active subjects will be an estimate of OR, together with associated 95% CI and p-value, comparing each M2951 dose group to placebo, based on a logistic model for the odds of SRI-4 response in the serologically active population, with M2951 dose group or placebo group as a factor and adjustment for covariates based on randomization strata. A test for trend in dose-response, using the same logistic model, will be reported as a supportive analysis.

Descriptive statistics for SRI-4 response in the serologically active subgroup, will be provided for each treatment group by time point.

#### Analysis of Other Secondary Efficacy Endpoints

Binary endpoints will be modeled via logistic regression, time to event endpoints will be modeled via Cox regression and tested via stratified log rank test, continuous endpoints

measured longitudinally (i.e., HRQoL change from baseline) will be analyzed using Mixed-effect Model for Repeated Measures (MMRM), and count endpoints (i.e., annualized flare rate) will be modeled via negative binomial regression, with treatment group as a factor, and adjusting for covariates defining randomization strata. Analysis of annualized flare rate will use the log of observation time (in years) as an offset in the model. Change in a binary endpoint between two time points will be analyzed via McNemar's test. The effect of treatment on change in a binary endpoint will be analyzed via logistic regression, with treatment group, time point, and interaction as predictors, and adjusting for covariates defining randomization strata. All tests of efficacy will be conducted at a two-sided  $\alpha$  level of 0.05, with p-values considered nominal unless generated as part of the tree gatekeeping multiple testing strategy as described in the Integrated Analysis Plan (IAP). P-values and the 95% CIs will be presented where applicable.

Analysis of Safety

Safety data for all treatment groups (M2951 dose groups, placebo group) will be listed and summarized using descriptive statistics.

**Table 1 Schedule of Assessments; Screening and Treatment Period (All Subjects), End of Study (Subjects Not Entering LTE Period)**

Trial Period	Screening	Visit Weeks During Treatment Period																		Follow-Up Visit 4 weeks Post-Last Dose a
		0	2	4	6	8	10	12	14	16	20	24	28	32	36	40	44	48	52/ EOT/Early Withdrawal	56/ Safety Follow- Up/End of Study
Trial Day	-28 to -1	1	15	29	43	57	71	85	99	113	141	169	197	225	253	281	309	337	365	393
Visit		Day 1	Wk 2	Wk 4	Wk 6	Wk 8	Wk 10	Wk 12	Wk 14	Wk 16	Wk 20	Wk 24	Wk 28	Wk 32	Wk 36	Wk 40	Wk 44	Wk 48	Wk 52	Wk 56
Visit window (±day)	+7	-	±3	±3	±3	±3	±3	±3	±3	±3	±3	±3	±3	±3	±3	±3	±3	±3	±3	+5
Informed consent	X																			
LTE informed consent																			X	
Inclusion/exclusion criteria	X	X b																		
Demographics and medical history c	X																			
Chest X-ray d	X																			
12-lead ECG	X	X						X				X				X			X	X e
Physical examination	X	X f	X g	X g		X g		X g		X g	X g	X	X h	X h	X h	X h	X h	X h	X	X g
Vital signs, weight, height i	X	X f	X	X		X		X		X	X	X	X	X	X	X	X	X	X	X
SFI, SLEDAI-2K, PGA, BILAG 2004, CLASI	X	X f	X i	X		X		X		X	X	X	X	X	X	X	X	X	X	X
SLICC/ACR Damage Index		X f																	X	
C-SSRS	X			X				X			X		X		X		X		X	X

Trial Period	Screening	Visit Weeks During Treatment Period																		Follow-Up Visit 4 weeks Post-Last Dose a
		0	2	4	6	8	10	12	14	16	20	24	28	32	36	40	44	48	52/ EOT/Early Withdrawal	
Trial Day	-28 to -1	1	15	29	43	57	71	85	99	113	141	169	197	225	253	281	309	337	365	393
Visit		Day 1	Wk 2	Wk 4	Wk 6	Wk 8	Wk 10	Wk 12	Wk 14	Wk 16	Wk 20	Wk 24	Wk 28	Wk 32	Wk 36	Wk 40	Wk 44	Wk 48	Wk 52	Wk 56
Visit window (±day)	+7	-	±3	±3	±3	±3	±3	±3	±3	±3	±3	±3	±3	±3	±3	±3	±3	±3	±3	+5
IMP administration k		Daily administration of IMP																		
Urinalysis and microscopy	X	X f	X	X		X		X		X	X	X	X	X	X	X	X	X	X	X
Routine hematology, chemistry m	X	X f	X	X		X		X		X	X	X	X	X	X	X	X	X	X	X
Supplementary LFTs n					X		X		X											
Total Ig Levels (IgG, IgA, IgM)	X	X f	X	X				X				X			X				X	X
CCI																				
Coagulation (INR, PTT)	X																			
HIV o , HCV, and HBV testing	X																			
Reflex testing for HBV DNA r	X			X		X		X		X	X	X			X			X	X	X
Serum pregnancy and FSH testing s	X																			
Serum β-D-glucan t	X																			
TSH	X																			

[figure not shown]
Trial Period	Screening	Visit Weeks During Treatment Period																		Follow-Up Visit 4 weeks Post-Last Dose a
		0	2	4	6	8	10	12	14	16	20	24	28	32	36	40	44	48	52/ EOT/Early Withdrawal	
Trial Day	-28 to -1	1	15	29	43	57	71	85	99	113	141	169	197	225	253	281	309	337	365	393
Visit		Day 1	Wk 2	Wk 4	Wk 6	Wk 8	Wk 10	Wk 12	Wk 14	Wk 16	Wk 20	Wk 24	Wk 28	Wk 32	Wk 36	Wk 40	Wk 44	Wk 48	Wk 52	Wk 56
Visit window (±day)	+7	-	±3	±3	±3	±3	±3	±3	±3	±3	±3	±3	±3	±3	±3	±3	±3	±3	±3	+5
Tuberculosis assessment f	X																			
Urine pregnancy test g		X f	X	X		X		X		X	X	X	X	X	X	X	X	X	X	X
UPCR	X	X f	X	X		X		X		X	X	X	X	X	X	X	X	X	X	X
SF-36v2, LupusQoL, FACIT- Fatigue, EQ-5D- 5L h		X		X		X		X		X		X		X		X			X	X
HRU				X		X		X		X	X	X	X	X	X	X	X	X	X	X
PGIC h				X		X		X		X		X		X		X			X	X
Dispense IMP		X	Dispense as needed, using IWRS																	
Dispense subject diary		X	Dispense as needed.																	
Concomitant medications / procedures	X	X	X	X	X	X	X	X	X	X	X	X	X	X	X	X	X	X	X	X
Adverse Events	X	X	X	X	X	X	X	X	X	X	X	X	X	X	X	X	X	X	X	X
CCI																				

Trial Period	Screening	Visit Weeks During Treatment Period																		Follow-Up Visit 4 weeks Post-Last Dose a
		0	2	4	6	8	10	12	14	16	20	24	28	32	36	40	44	48	52/ EOT/Early Withdrawal	
Trial Day	-28 to -1	1	15	29	43	57	71	85	99	113	141	169	197	225	253	281	309	337	365	393
Visit		Day 1	Wk 2	Wk 4	Wk 6	Wk 8	Wk 10	Wk 12	Wk 14	Wk 16	Wk 20	Wk 24	Wk 28	Wk 32	Wk 36	Wk 40	Wk 44	Wk 48	Wk 52	Wk 56
Visit window (±day)	+7	-	±3	±3	±3	±3	±3	±3	±3	±3	±3	±3	±3	±3	±3	±3	±3	±3	±3	+5
Immunological Assessments																				
Anti-dsDNA, Complement (C3, C4), CRP	X	X f		X		X		X		X	X	X	X	X	X	X	X	X	X	X
ANA, anti-Sm	X																			
Autoantibodies		X									X								X	X

**Exploratory Biomarkers**

Trial Period	Screening	Visit Weeks During Treatment Period																		Follow-Up Visit 4 weeks Post-Last Dose a
		0	2	4	6	8	10	12	14	16	20	24	28	32	36	40	44	48	52/ EOT/Early Withdrawal	56/ Safety Follow- Up/End of Study
Trial Day	-28 to -1	1	15	29	43	57	71	85	99	113	141	169	197	225	253	281	309	337	365	393
Visit		Day 1	Wk 2	Wk 4	Wk 6	Wk 8	Wk 10	Wk 12	Wk 14	Wk 16	Wk 20	Wk 24	Wk 28	Wk 32	Wk 36	Wk 40	Wk 44	Wk 48	Wk 52	Wk 56
Visit window (±day)	+7	-	±3	±3	±3	±3	±3	±3	±3	±3	±3	±3	±3	±3	±3	±3	±3	±3	±3	+5

ACR = American College of Rheumatology, ALT = alanine aminotransferase, ANA = Antinuclear Antibody(ies), Anti-dsDNA = Anti-Double-Stranded Deoxyribonucleic Acid, Anti-Sm = anti-Smith antibody, AST = aspartate aminotransferase, BILAG = British Isles Lupus Assessment Group, BP = blood pressure, CCI [redacted], CLASI = Cutaneous Lupus Erythematosus Disease Area and Severity Index, CRP = C-Reactive Protein, C-SSRS = Columbia-Suicide Severity Rating Scale, DNA = deoxyribonucleic acid, ECG = Electrocardiogram, EOT = End of Treatment, EQ-5D-5L = EuroQoL 5 Dimension 5 Levels, FACIT = Functional Assessment of Chronic Illness Therapy, GGT = γ-Glutamyl-transferase, Ig = Immunoglobulin, IMP = Investigational Medicinal Product, IWRS = Interactive Web Response System, HBV = Hepatitis B Virus, HCV = Hepatitis C Virus, HIV = Human Immunodeficiency Virus, HRQoL = Health Related Quality of Life, HRU = Health Resource Utilization, INR = International Normalized Ratio, LFT = liver function test, LTE = long-term extension, LupusQoL = Lupus Quality of Life, mRNA = messenger Ribonucleic Acid, CCI [redacted] PCR = polymerase chain reaction, PGA = Physician's Global Assessment, PGIC = Patient Global Impression of Change, CCI [redacted], PTT = Partial Thromboplastin Time, SF-36v2 = Medical Outcomes Study 36-Item Short Form Health Survey, SFI = SLEDAI Flare Index, SLEDAI-2K = Systemic Lupus Erythematosus Disease Activity Index-2000, SLICC = Systemic Lupus International Collaborating Clinics, TB = tuberculosis, TSH = Thyroid Stimulating Hormone, UPCR = Urine Protein To Creatinine Ratio, Wk = Week.

- a Safety Follow-Up Visit will be conducted at four weeks after the last dose of IMP for subjects who have been discontinued from IMP or have completed the 52-week Treatment Period, unless subjects have entered the LTE period.
- b Subject eligibility to be confirmed on Day 1 prior to randomization.
- c Medical history includes documentation of SLE classification criteria, SLE medical history, medications, and surgery/procedures (see Section 7.2.1).
- d The results of a chest X-ray performed within three months prior to the Screening Visit (if available) are acceptable, provided there is no reason to suspect any clinical changes, per Investigator discretion.
- e Only required if change noted at Wk52/EOT, when compared to Baseline ECG.

- f Predose sample/procedure to be collected/performed before the first daily dose.
- g Abbreviated physical examination at these visits (see Section 7.4.4.2).
- h Abbreviated physical examination may be performed at Primary Investigator discretion, as required to fully obtain information needed for the BILAG and/or SLEDAI assessments, if scheduled, as well as required to fully evaluate any subject complaints or adverse events.
- i Vital signs include arterial BP, pulse rate, respiratory rate, and body temperature. Height will be measured at Screening only. Body weight will be measured with a balance beam scale, if possible. Pulse rate and BP will be measured after 10 minutes rest in the semisupine position with the subject's arm unconstrained by clothing or other material. The BP should be assessed on the same arm for each subject throughout the study.
- j Only CLASI assessed at Week 2.
- k On Study Visit Days, IMP should be administered during the Study Visit; otherwise, IMP should be self-administered at home at a set time each day (every 12 hours ± 2 hours). Investigational medicinal product administration at Week 52 will only occur for subjects rolling over into the LTE.
- l A Quantiferon test will be performed centrally. Prior TB testing results must be entered into the eCRF.
- m See Table 11 for list of clinical laboratory evaluations.
- n Supplementary LFTs include AST, ALT, alkaline phosphatase, GGT, and bilirubin.
- C** [REDACTED]
- C** [REDACTED]
- p To be collected at Screening only in subjects who have previously received B cell depleting therapy (see Exclusion Criterion 33, in Section 5.3.2).
- q HIV testing will be performed locally.
- r For subjects who are negative for hepatitis B surface antigen (HBsAg) but are anti-hepatitis B surface antibody positive and/or anti-hepatitis B core antibody positive, an HBV DNA PCR reflex test is to be completed at screening. If the subject enters the study with positive HBV DNA negative OR has detectable HBV DNA < 20 IU/mL only, additional HBV DNA PCR testing must be performed (see Exclusion criteria 20, in Section 5.3.2).
- s For women of childbearing potential or who are postmenopausal see inclusion criterion 7. A follicle-stimulating hormone (FSH) must be drawn at Screening if necessary to confirm postmenopausal status. The urine pregnancy test being used at all time points in this study must be a highly sensitive urine pregnancy test.
- t For Japan only.
- u HRQoL Questionnaires should be completed before any other procedures are performed.

**CCI**

**CCI**

**Table 2 Schedule of Assessments – Optional Long-Term Extension Period**

LTE Trial Period	Visit Weeks During LTE Treatment Period														Follow-Up Visit 4 weeks Post-Last Dose a
	0	2	4	6	8	10	12	14	16	24	40	52	76	Week 104/ LTE EOT/Early Withdrawal	Week 108/ Safety Follow- Up/LTE End of Study
Trial Day	1	15	29	43	57	71	85	99	113	169	281	365	545	745	774
Visit	Day 1 b	Wk 2	Wk 4	Wk 6	Wk 8	Wk 10	Wk 12	Wk 14	Wk 16	Wk 24	Wk 40	Wk 52	Wk 76	Wk 104	Wk 108
Visit window (±day)	-	±3	±3	±3	±3	±3	±3	±3	±3	±7	±7	±7	±7	±7	+5
Informed Consent	X														
Verify subject remains eligible for the study (no prohibited medication, etc.)	X														
Vital signs, weight c	X		X		X		X		X	X	X	X	X	X	X
12-lead ECG	X						X			X		X	X	X	X d
Physical examination	X		X e		X e		X e		X e	X e	X e	X	X e	X	X e
Routine hematology, urinalysis, chemistry	X		X		X		X			X	X	X	X	X	X
Urine microscopy	X									X		X		X	
Supplementary LFT labs		X		X		X		X	X						
Total Ig Levels (IgG, IgA, IgM)	X		X		X		X			X	X	X	X	X	X
CCI															
Urine pregnancy test g	X		X		X		X		X	X	X	X	X	X	X
Urine pregnancy test kit dispensation g									X	X	X	X	X		
Reflex testing for HBV DNA h	X		X		X		X		X	X	X	X	X	X	X
UPCR	X									X		X		X	
IMP dispensation i	X	Dispense as needed, using IWRS and complete compliance documentation													
IMP administration j	Daily Administration of Evobrutinib														

LTE Trial Period	Visit Weeks During LTE Treatment Period														Follow-Up Visit 4 weeks Post-Last Dose a
	0	2	4	6	8	10	12	14	16	24	40	52	76	Week 104/ LTE EOT/Early Withdrawal	Week 108/ Safety Follow- Up/LTE End of Study
Trial Day	1	15	29	43	57	71	85	99	113	169	281	365	545	745	774
Visit	Day 1 b	Wk 2	Wk 4	Wk 6	Wk 8	Wk 10	Wk 12	Wk 14	Wk 16	Wk 24	Wk 40	Wk 52	Wk 76	Wk 104	Wk 108
Visit window (±day)	-	±3	±3	±3	±3	±3	±3	±3	±3	±7	±7	±7	±7	±7	+5
C-SSRS	X						X			X		X	X	X	X
SFI, SLEDAI-2K, PGA, BILAG 2004, CLASI	X									X		X		X	
SLICC/ACR Damage Index	X									X		X		X	
SF-36v2, LupusQoL, FACIT-Fatigue, EQ-5D-5L k	X									X		X		X	
PGIC k	X									X		X		X	
HRU	X		X		X		X		X	X	X	X	X	X	X
Concomitant medications / procedures	X	X	X	X	X	X	X	X	X	X	X	X	X	X	X
Adverse Events	X	X	X	X	X	X	X	X	X	X	X	X	X	X	X
CCI															
Immunological Assessments															
Anti-dsDNA Complement (C3, C4), CRP	X									X		X		X	
ANA and other Autoantibodies	X									X		X		X	

ACR = American College of Rheumatology, ANA = Antinuclear Antibody(ies), Anti-dsDNA = Anti-Double-Stranded Deoxyribonucleic Acid, BILAG 2004 = British Isles Lupus Assessment Group 2004, CLASI = Cutaneous Lupus Erythematosus Disease Area and Severity Index, C-SSRS = Columbia-Suicide Severity Rating Scale, D = day, DNA = deoxyribonucleic acid, ECG = Electrocardiogram, EOT = End of Treatment, EQ-5D-5L = EuroQoL 5 Dimension 5 Levels, FACIT = Functional Assessment of Chronic Illness Therapy, HBsAg = hepatitis B surface antigen, HBV = Hepatitis B Virus, HRU = Health Resource Utilization, Ig = Immunoglobulin, IMP = Investigational Medicinal Product, LFT = liver function test, LTE = Long-Term Extension, LupusQoL = Lupus Quality of Life, PGA = Physician's Global Assessment, PGIC = Patient Global Impression of Change, CCI [REDACTED], SFI = SLEDAI Flare Index, SLEDAI-2K = Systemic Lupus Erythematosus Disease Activity Index-2000, SLICC = Systemic Lupus International Collaborating Clinics, SoA = Schedule of Assessments, UPCR = Urine Protein To Creatinine Ratio, Wk = Week, WOCPB = women of childbearing potential.

- a Safety Follow-Up Visits will be conducted at four weeks after the last dose of IMP for subjects who have been discontinued from IMP or have completed the LTE Treatment Period.
- b The LTE D1 visit is the EOT/Wk 52 visit from the DBPC Period unless a subject rollover more than four weeks after the Wk 52/EOT visit. If a subject exceeds the four weeks due to unanticipated causes (e.g., regulatory approval delay), prior approval from the Medical Monitor is required and the subject will need to complete the LTE D1 visit (see Section 7.1.3).
- c Vital signs including weight, oral temperature, seated blood pressure, pulse rate, and respiratory rate.
- d Only required if change noted at Wk 104/EOT, when compared to Baseline ECG.
- e Abbreviated physical examination may be performed at Primary Investigator discretion, as required to fully obtain information needed for the BILAG and/or SLEDAI assessments, if scheduled, as well as required to fully evaluate any subject complaints or adverse events (see Section 7.4.4.2).
- f [REDACTED]
- g The urine pregnancy test being used at all time points in this study must be a highly sensitive urine pregnancy test. In-between visit urine pregnancy tests will be dispensed and performed at home per SOA (Table 3) for WOCPB. The site staff will confirm completion of the home pregnancy testing and discuss results (Section 7.1.3).
- h Additional HBV DNA PCR testing must be performed for subjects who entered the study with negative HBsAg and positive for anti-hepatitis B surface antibody and/or anti-hepatitis B core antibody with an HBV DNA negative OR detectable HBV DNA < 20 IU/mL only.
- i The IMP will be dispensed per IWRS and IMP compliance documented using pill counts. All remaining IMP will be collected at Week 104 for all subjects.
- j IMPs will be self-administered at a set time each day ( $\pm$  2 hours).
- k HRQoL Questionnaires should be completed before any other procedures are performed.

CCI [REDACTED]

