### **Optional Open-Label Long-Term Extension Period**

Subjects who completed the 52-week DBPC Treatment period will be offered participation in the 104-week open-label, LTE Period of the study. The purpose of the LTE Period is to allow all the subjects with the opportunity to receive active treatment with M2951 and to collect long term safety and efficacy data. The Investigator should review the optional LTE Period with the subject prior to the DBPC Week 52 visit. Signed consent will be obtained prior to participation in the LTE Period. The DBPC Week 52/EOT Visit will be considered the LTE Day 1 Visit. The Safety Follow-Up Visit will be deferred until treatment is stopped in the LTE Period, due to either a subject's premature withdrawal/early termination from the LTE, termination of the study by the Sponsor, or completion of the LTE treatment period.

In some cases, due to Institutional Review Board (IRB)/Independent Ethics Committee (IEC) approval, regulatory-specific, or other administrative delays, a subject may experience a treatment gap between the IMP last dose received in the DBPC Period (Week 52/EOT visit) and the start of the LTE IMP treatment. Upon Principal Investigator (PI) request, these subjects may still be able to enroll in the LTE with approval from Merck/EMD Serono, on a case-by-case basis. If the day of rollover to the LTE occurs after the DBPC Week 56/EOS visit, all assessments noted at the LTE Day 1 visit will need to be completed. For subjects that rollover after the Week 52/EOT visit but prior to their scheduled Week 56/EOS visit, concomitant medications and AEs will need to be reviewed and updated, and the PI will need to ensure that the subject remains eligible for the study. No other additional assessments other than dispensing of IMP will need to be completed.

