### 7.2.3 Other Baseline Assessments

The term ‘Baseline’ in this protocol is defined as Day 1, predose. Baseline measurements, such as vital signs, a complete physical examination, clinical laboratory parameters, 12-lead ECG, HRQoL assessments (SLEDAI Flare Index [SFI], SLEDAI-2K, PGA, C-SSRS, BILAG 2004, CLASI, SLICC/ACR damage index), and PD parameters will be assessed as indicated in the SOA (Table 1). The HRQoL assessments on Day 1 are to be completed after inclusion/exclusion criteria are reviewed, verified, and the subject is randomized.

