## 7.4.4 Vital Signs, Physical Examinations, and Other Assessments

### 7.4.4.1 Vital Signs

Vital signs, including blood pressure (BP), pulse rate, respiratory rate, weight, and oral temperature will be assessed predose at all study visits (Table 1). Height will be measured at Screening only.

A semiautomated pulse rate and BP recording device with an appropriate cuff size will be utilized. Pulse rate and BP will be measured after 10 minutes rest in the semisupine position with the subject's arm unconstrained by clothing or other material. The BP should be assessed on the same arm for each subject throughout the study.

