### 8.5.4 Analysis of Safety

Adverse events will be summarized by treatment group, severity, and relationship to IMP. Serious AEs, AEs leading to treatment discontinuation, and AEs leading to treatment withdrawal will be summarized by treatment group.

Adverse events will be coded according to the medical dictionary for regulatory activities (MedDRA). The severity of AEs will be graded using the NCI-CTCAE v4.03 grading scale (Hahn 2012).

The number and percentage of subjects experiencing one or more treatment-emergent AEs (TEAEs) will be summarized according to the MedDRA system organ classes and preferred terms by treatment group, relationship to IMP, and severity.

Summary statistics will be used to present observed values and changes from Baseline in continuous laboratory, vital sign, and ECG data. Shift tables will be used to present changes in categorical laboratory parameters. Figures will be generated as needed to assist safety evaluation.

Values for all safety variables will be listed by subject and time point.

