## 8.5.6 Analysis of LTE Endpoints

Efficacy and HRQoL data collected during the LTE Period will be summarized. Details will be provided in the IAP.

Safety data collected during the LTE Period will be analyzed as described in Section 8.5.4.

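### The extension schedule specifies seated blood pressure and the rest of the protocol semisupine, so extension change from Baseline would mix posture with treatment

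*Protocol*

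**What the plan says.** **Double-blind period.** Section 7.4.4.1 states: "Pulse rate and BP will be measured after 10 minutes rest in the semisupine position". Table 1 footnote i carries the same rule. Section 7.4.4.1 also asks for constant technique: "The BP should be assessed on the same arm for each subject throughout the study". On scope, it says that vital signs "will be assessed predose at all study visits (Table 1"; the citation ends there and Table 2 is not named.

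**Extension.** Table 2 footnote c, which governs vital signs at all LTE visits, reads: "Vital signs including weight, oral temperature, seated blood pressure, pulse rate, and respiratory rate". It gives no rest period. The word seated is attached to blood pressure, and the position for pulse is left unclear.

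**Analysis.** Under Section 7.2.3 the term Baseline "in this protocol is defined as Day 1, predose". Section 8.5.6 says: "Safety data collected during the LTE Period will be analyzed as described in Section 8.5.4". Section 8.5.4 in turn says: "Summary statistics will be used to present observed values and changes from Baseline in continuous laboratory, vital sign, and ECG data".

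**Shared visit.** Section 5.1 states: "The DBPC Week 52/EOT Visit will be considered the LTE Day 1 Visit".

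**The concern.** Two measurement methods are specified for one variable, and nothing in the protocol reconciles them. The boundary between the methods is entry to the open-label extension. At that point former placebo subjects receive M2951 for the first time, and former lower-dose subjects move to 50 mg twice daily or the eventual Phase III dose. Vital signs are a listed LTE safety endpoint (Section 8.3.4), and the extension has no concurrent control group in which a change of technique would cancel. A reader of the LTE tables could take a step in mean blood pressure for a treatment change when part or all of it is posture. The reverse is also possible: a real change could be masked.

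**Working it through.** No figure in the plan can be reproduced here. The check compares the passages and follows the data into the analysis.

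**1. The two rules side by side**

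| | Table 1 footnote i and Section 7.4.4.1 | Table 2 footnote c |
|---|---|---|
| Blood pressure position | semisupine | seated |
| Pulse position | semisupine | unclear |
| Rest before reading | 10 minutes | not stated |
| Same arm | yes, throughout the study | not repeated |

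Sections 7.4.4.2 (physical examination) and 7.4.4.3 (ECG) cite both Table 1 and Table 2, whereas Section 7.4.4.1 cites Table 1 only. This is consistent with an oversight when the extension schedule was added. The rationale shown for Amendment 14 gives no reason for a change of posture.

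**2. What change from Baseline then contains**

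Let d be a subject's seated minus semisupine difference in blood pressure, and T(t) the true change since Day 1 at LTE visit t. Baseline is semisupine (Section 7.2.3 with Table 1) and the LTE reading is seated (Table 2), so:

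observed LTE change = T(t) + d.

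The documents give no value, sign or standard deviation for d, so its size cannot be derived from them.

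**3. How many readings are involved**

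- Planned LTE subjects (Section 8.1): 0.80 × 432 = 345.6, about 346.
- Former placebo subjects, assuming equal rollover across the four arms: 346 / 4 = 86.5, so about 86.
- Table 2 schedules vital signs at LTE Day 1 and at Weeks 4, 8, 12, 16, 24, 40, 52, 76, 104 and 108. That is 11 visits, 10 of them after Day 1 and governed by footnote c alone.

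**4. The shared visit**

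The Week 52 reading is semisupine under Table 1 and seated under Table 2. Subjects who roll over after the Week 56 visit repeat all LTE Day 1 assessments (Section 5.1), and Table 2 alone then applies. Readings labelled LTE Day 1 could therefore be in different postures in different subjects.

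**5. Can posture be separated from treatment?**

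Partly. Suppose the Week 52 reading was semisupine. The step from Week 52 to an LTE visit is then:

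- former 50 mg twice daily: d + time trend, because the dose does not change at rollover;
- former placebo: d + time trend + effect of starting M2951.

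If d and the time trend are alike in the two groups, the difference between these steps removes d. This check fails if the Week 52 posture varies between subjects, and it weakens once subjects are switched to a Phase III dose. It also compares only those who chose to continue. The Week 108 reading, four weeks after the last dose and under the same footnote, is d + any time trend + any residual treatment effect. It is informative about d but does not isolate it.

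**The case against.** The strongest reply is that this is a wording mismatch with limited reach, and several parts of that reply stand.

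- **Posture and drug effect are not strictly inseparable.** A reader might infer that a posture shift could never be told apart from an effect of M2951. The documents do not support that. One randomised arm already takes 50 mg twice daily and keeps that dose at rollover, and Week 108 provides an off-drug reading under the same footnote. Three of the four arms have also had 52 weeks of M2951 before the extension. These checks are partial (step 5), but they exist.
- **The primary safety comparison is intact.** A reader might infer that a primary endpoint is compromised, because vital signs are among the primary safety endpoints. Table 1 sets one method for all four arms in the double-blind period, and the doubt about Week 52 is not specific to any arm.
- **A shift is not established.** Section 7.4.4.1 refers to all study visits and to constant technique throughout the study, and footnote c can be read as a list of parameters. Sites that follow Section 7.4.4.1 in the extension would produce no shift. What is established is an unresolved contradiction, and one of its two readings produces the mixture.
- **Baseline may be redefined.** Section 8.5.1 leaves further Baseline definitions to the Integrated Analysis Plan, and a seated LTE Baseline would remove d. That works only if LTE Day 1 was taken seated in every subject or its posture was recorded, and step 4 shows that the protocol secures neither.
- **The analysis is descriptive.** Section 8.5.4 plans summary statistics without a test, so no error rate is affected. A biased mean change is still a biased description of an LTE safety endpoint.
- **Changing technique mid-extension has a cost.** Subjects already measured seated would have a new break within the LTE. This is correct, and the fix has to provide for it.

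**Conclusion.** The contradiction is in the current text and should be corrected. Under the protocol's own Baseline and LTE safety analysis, following Table 2 as written makes LTE change in blood pressure the sum of a posture difference and any treatment change. The size and direction of the posture difference are unknown. The reach is up to 10 scheduled readings per subject after LTE Day 1 in about 346 planned subjects, plus an ambiguous reading at the shared visit. For pulse, the finding is only that the LTE position and rest period are unclear.

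The conclusion rests on two conditions: that sites follow footnote c, and that Day 1 predose remains the Baseline for LTE summaries. It does not extend to the randomised double-blind comparison. Nor does it show that extension data will display a false drug effect; it shows an avoidable risk of confounding that the design can only partly check.

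**What to change.** 1. Reword Table 2 footnote c to match Section 7.4.4.1 and Table 1 footnote i: blood pressure and pulse semisupine, after 10 minutes of rest, with blood pressure on the same arm.
2. Add Table 2 to the citation in Section 7.4.4.1.
3. State that this one method applies at the shared Week 52/LTE Day 1 visit, and at a repeated LTE Day 1 visit for late rollovers.
4. If LTE readings have already been taken seated, record posture at each reading and summarise change only against a Baseline taken in the same posture. Where a subject has no such Baseline, present observed values only.

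The cost is one footnote, one cross-reference and, only if seated readings exist, a posture field. Section 7.4.4.3 already requires ECGs semisupine after 10 minutes of rest. Table 2 pairs an ECG with vital signs at LTE Day 1 and Weeks 12, 24, 52, 76 and 104, so 6 of the 11 vital-sign visits already include that position and rest. The remaining visits need only the rest period.
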